### **3.3. Study Endpoints**

#### **3.3.1. Primary Efficacy Endpoint**

The primary efficacy endpoint is the “strength” of alcohol craving VAS score (item 1 below) upon presentation of the first alcohol cue at Week 2 – after one week of investigational product treatment.

Confirmatory secondary endpoints include the VAS score for the other 3 VAS scales (items 2 through 4 below) for the first alcohol cue and the average score of the 4 VAS craving items; and the difference score (alcohol craving VAS scores minus the water craving VAS score).

The beverage liking VAS item is also a confirmatory secondary endpoint. The 4 VAS craving items in the order of presentation are:

1. How strong is your craving to drink alcohol? - note this is the primary efficacy endpoint.
2. Having a drink would make things just perfect.
3. If I could drink alcohol now, I would drink it.
4. It would be hard to turn down a drink right now.

The beverage liking item is: How much did you like the beverage just given to you?

#### **3.3.2. Secondary Efficacy Endpoints**

Secondary efficacy endpoints will be analyzed over the last 4 weeks of the treatment period of treatment.

1. Percentage of subjects with no heavy drinking days. A “heavy drinking day” is 4 or more drinks per drinking day for women and 5 or more drinks per drinking day for men.
2. Percentage of subjects abstinent from alcohol
3. Percentage of subjects with at least a WHO 2-level decrease in alcohol consumption
4. Percentage of subjects with at least a WHO 1-level decrease in alcohol consumption
5. Percentage of days abstinent per week
6. Percentage of heavy drinking days per week
7. Percentage of very heavy drinking days per week. A “very heavy drinking day” is 8 or more drinks per drinking day for women and 10 or more drinks per drinking day for men.
8. Weekly mean number of drinks per week
9. Weekly mean drinks per drinking day
10. Cigarettes smoked per week among smokers
11. Percentage of subjects with no nicotine use among those reporting nicotine use at baseline
12. Alcohol craving score (PACS)
13. Sleep quality (PSQI) score

14. Profile of Mood States (POMS) score
15. PROMIS Alcohol Negative Consequences Score

### **3.3.3. Safety Endpoints**

1. Vital signs
2. Body weight
3. Clinical laboratory parameters
4. BAC by breathalyzer
5. Urine drug tests
6. AEs
7. ECG results
8. CIWA-AR scores
9. Frequency of subjects with suicidal ideation at any time during the treatment period (C-SSRS)
10. Concomitant medication use
11. ACQ-SF-SR score (pre- and post-cue response sessions)

### **3.3.4. Compliance**

Compliance will be assessed using the AiCure smart phone application and by tablet counts of returned blister packs at regular clinic visits. In addition, blood will be collected to determine plasma levels of ASP8062 and its metabolites. Compliance will be calculated as the percentage of investigational products taken as prescribed and by the total amount of study drug consumed. Participation in study visits will be evaluated as the percentage of subjects with complete drinking data. Compliance determined by ASP8062 plasma levels will be reported as number and percentage of subjects with a level above the limit of detection at each time point.

#### 4. DEFINITION OF ANALYSIS SETS

The study analysis populations will consist of the following:

**Modified Intention-to-Treat (mITT) Analysis Set:** The mITT set is defined as subjects randomized to participate in the study that took at least one dose of investigational product and had a non-missing VAS craving primary endpoint.

**Evaluable Analysis Set:** The evaluable analysis set for the secondary endpoints is defined as those subjects randomized to the study who took at least 1 tablet per day for at least 80% of days in Weeks 1-6.

**Safety Analysis Set:** The safety analysis set includes all subjects who took at least one dose of investigational product.

The analysis of the primary and confirmatory efficacy endpoints will be conducted on both the mITT and evaluable analysis sets. All secondary endpoint analyses will be performed on the mITT set. Weekly percentage heavy drinking days, mean number of drinks per week, and PACS scores will also be performed on the evaluable analysis set. Safety analyses will be conducted on the safety analysis set.

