### **5.2.5. Percentage of Subjects with No Heavy Drinking Days and Percentage of Subjects Abstinent from Alcohol**

The percentage of subjects with no heavy drinking days is the number of subjects that have no heavy drinking days during the period of interest divided by the number of subjects with at least one day of non-missing drinking data during the period of interest, multiplied by 100.

The percentage of subjects abstinent from alcohol is calculated similarly, except the numerator is the number of subjects that have no drinking days during the period of interest.

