## **9.5. Handling of Missing Data**

The primary endpoint of craving cannot be imputed; likewise, for the other craving questions given during the human lab session. Secondary endpoints analyzed with mixed effects or logistic regression models are capable of handling missing data, so no imputation will be utilized. PROMIS scores are analyzed using ANCOVA which cannot handle missing data; therefore, only subjects with an assessment during the treatment period will be used and no imputation.

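### Requiring a cue-session score for mITT can drop usable data from every Weeks 3-6 secondary endpoint, and it empties the early rows of the only by-week dropout table

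*SAP*

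**What the plan says.** SAP section 4 and the protocol synopsis define mITT as randomised subjects who "took at least one dose of investigational product and had a non-missing VAS craving primary endpoint". SAP section 4 alone then assigns the secondary endpoints: "All secondary endpoint analyses will be performed on the mITT set". SAP 9.4.3 sets their window as Weeks 3 to 6. SAP 9.5 explains why nothing is imputed: "Secondary endpoints analyzed with mixed effects or logistic regression models are capable of handling missing data, so no imputation will be utilized".

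The other efficacy set is introduced with a stated purpose: "The evaluable analysis set for the secondary endpoints is defined as those subjects randomized to the study". Entry depends on dosing over the whole treatment period, and a member is someone that "took at least 1 tablet per day for at least 80% of days in Weeks 1-6". It does not require a cue score. SAP section 4 nevertheless says: "The analysis of the primary and confirmatory efficacy endpoints will be conducted on both the mITT and evaluable analysis sets". It adds: "Weekly percentage heavy drinking days, mean number of drinks per week, and PACS scores will also be performed on the evaluable analysis set".

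SAP 9.2 and 9.7 promise dropout over time, by week and by arm. The only shell that does this is Table 14, which is headed for mITT subjects and starts at Week 1. Its footnote counts a subject as a dropout once TLFB and other data stop. Listings 14, 15, 17, 18, 19 and 27 are also mITT only, although SAP 9.1 says all data will be listed.

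**The concern.** The cue score is a post-randomisation condition that matters only to the cue endpoints. Drinking, PACS, PSQI, POMS, PROMIS and nicotine outcomes do not depend on it. The plan also expects drinking data from people who may have no cue score: SAP 5.2.6 lets the TLFB be recovered at a later visit after a missed one, and SAP 5.2.1 provides for phone questions to withdrawn subjects until the end of treatment. Anyone in that position is removed before a model is fitted, so the missing-data argument in SAP 9.5 never reaches them.

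Three things are at stake. Precision is lost on every secondary endpoint those subjects could inform. Bias could arise if missing the session differs by arm and is related to outcome. And the dropout table would report no loss in Weeks 1 and 2 whatever happened, although retention is a named secondary objective.

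For the evaluable set, dosing after the session helps decide who enters an analysis of a score already recorded.

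**Working it through.** **Inputs from the documents.** 60 subjects, 30 per arm (SAP section 7). A maximum of 42 tablets (Table 2 shell), which agrees with 6 weeks × 7 days. An 80% threshold over Weeks 1-6 (SAP section 4). A cue session in Week 3, Days 15-21 (Schedule of Assessments). Dosing at bedtime (protocol synopsis). No missed-session or dropout rate is stated, so those below are assumptions.

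**1. Who is removed.** Set SAP section 4 beside SAP 5.2.1 and 5.2.6: a dosed subject with no cue score can have Weeks 3-6 data and still be outside mITT. The sets are also not nested. A subject with 34 or more doses who missed the session counts in the evaluable analyses of heavy drinking days, drinks per week and PACS, but not in the mITT analyses of the same endpoints.

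**2. Precision (assumed losses m, each with full data).** The standard error of a difference is proportional to √(1/n₁ + 1/n₂).

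- Equal loss by arm, √(60/(60−m)) − 1: m = 3, √(60/57) − 1 = 2.6%; m = 6, √(60/54) − 1 = 5.4%; m = 12, √(60/48) − 1 = 11.8%.
- All loss in one arm, √[(1/(30−m) + 1/30)/(2/30)] − 1: m = 3, 2.7%; m = 6, 6.1%; m = 12, 15.5%.

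The cost is smaller if the lost subjects would have given only part of the four weeks. It is nil for the weekly endpoints if they would have answered only the two phone questions. The figures do not apply to the baseline-smoker or nicotine-user subsets, whose size is unknown.

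**3. Table 14.** Membership of mITT requires a score at the session. With a Week 3 session, no member can have stopped giving data in Weeks 1 or 2, so both rows are zero by construction. The Week 3 row counts only losses after the session.

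- Assume 6 of 60 leave before the session and 6 after. Table 14 shows 6/(60−6) = 11.1% cumulative dropout, against 12/60 = 20.0% of randomised subjects.
- Assume one arm loses 6 of 30 before the session, the other none, and each loses 3 after. True dropout is 9/30 = 30% against 3/30 = 10%; Table 14 shows 3/24 = 12.5% against 3/30 = 10.0%.

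**4. Evaluable set on cue endpoints.** 0.8 × 42 = 33.6, so 34 dosing days are needed (34/42 = 81.0%) and 8 may be missed. For a session on Day d, d−1 doses come before it and 43−d after.

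- Share of doses after the session, (43−d)/42: Day 15, 28/42 = 66.7%; Day 21, 22/42 = 52.4%.
- Lowest pre-session compliance that can still qualify, (d−9)/(d−1): Day 15, 6/14 = 42.9%; Day 17, 8/16 = 50.0%; Day 21, 12/20 = 60.0%.
- A subject fully dosed to Day 33 who then stops has 33/42 = 78.6% and is excluded.

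**5. Shells.** The efficacy shells on the evaluable set are odd-numbered Tables 35 to 65: (65−35)/2 + 1 = 16, all cue tables. None of Tables 66-109 uses the set, although SAP section 4 promises three such analyses. Listing 17 is the only listing of CIWA-AR, which SAP 5.3 classes as a safety endpoint, yet it is restricted to mITT.

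**The case against.** The rule is explicit and pre-specified, these are secondary endpoints in a 60-subject Phase 2a study, and a common set suits the planned look at how cue and naturalistic outcomes relate (SAP 9.9.1). Missed sessions are also limited by design: the visit has a 7-day window, and a Week 2 call is to remind subjects of it. Subjects who continue without a cue score may be few. All of this stands, and it is why the size of the problem is left open.

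Early losses are not wholly hidden. Table 1 gives the mITT count by arm for all randomised subjects, Listing 1 the day of withdrawal, and Listing 5 the reason for exclusion from mITT. Table 120 summarises CIWA-AR of 10 or more on the safety set. These show part of the loss, but none gives dropout by week and arm.

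A reader might infer that SAP 5.2.5 contradicts section 4, because its denominator is "the number of subjects with at least one day of non-missing drinking data during the period of interest". It need not: the denominator can be read as applying within mITT. A reader might also take the secondary results to be biased, or the equal-loss figures as an upper bound. The documents give no rate to support the first, and one-arm loss exceeds the second. Nor is the primary estimate in question: for that endpoint, mITT is simply the complete-case set.

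**Conclusion.** The concern holds in a limited form. Using mITT for the Weeks 3-6 endpoints is a poor choice of set. Its effect depends on how many dosed subjects lack a cue score but have other data, which cannot be known from the documents. The standard-error figures are illustrations under assumed losses, not bounds.

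Table 14 is wrong as written for a Week 3 session, because it cannot deliver what SAP 9.2 and 9.7 promise. That conclusion needs no assumption about rates; only the percentages in the examples do. Listing 17 is on the wrong set for a safety endpoint.

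The evaluable-set point is firm on the arithmetic but lesser in weight, since it touches only the supportive cue analyses.

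Session timing is a separate defect: SAP 3.3.1 places the session in Week 2 after one week of treatment, while the protocol synopsis and the Schedule of Assessments place it in Week 3. The passages must be reconciled. With a Week 2 session, only the Week 1 row of Table 14 would necessarily be zero.

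**What to change.** Make these changes before unblinding.

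1. Use one fixed set for the secondary endpoints: all randomised subjects with at least one dose (the existing safety set, analysed as randomised). Each model then uses the data available for its endpoint. Edit SAP section 4, 9.3 and 9.4.3.3 (which fixes the smoking sample as mITT). Re-head Tables 15 and 66-109, the secondary-endpoint figures, and Listings 14, 15, 18, 19 and 27. Restore the safety-set baseline summary, which the protocol synopsis promises and SAP 9.3 omits.
2. Run Table 14 on all randomised subjects.
3. Put Listing 17 on the safety set.
4. For the supportive cue analyses (odd-numbered Tables 35-65), define compliance only on days before the session. Keeping 80% would require 12 of 14 days for a Day 15 session and 16 of 20 for Day 21. Label the set as supportive, because it still selects on adherence after randomisation. Keep the Weeks 1-6 rule for secondary endpoints, and add the three missing evaluable shells.

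The cost is SAP text, any matching protocol wording, one new population flag for cue compliance, re-headed shells and a few added tables. No new data are collected. The downside is that Ns will differ between primary and secondary tables, and there are more shells to validate.

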## **5. ASSESSMENT AND JUSTIFICATION OF STUDY ENDPOINTS**

### **5.1. Alcohol Craving Visual Analog Scales**

Alcohol craving in response to a water and typical alcohol beverage cue is assessed using 4 individual VAS items adapted from the ACQ ([Singleton-1994](#)).

The VAS craving scale items include in the following order:

1. How strong is your craving to drink alcohol?
2. Having a drink would make things just perfect.
3. If I could drink alcohol now, I would drink it.
4. It would be hard to turn down a drink right now.

Anchors (scores) for items 1, 3, and 4 are: Strongly Disagree (0) to Strongly Agree (20).

Anchors (scores) for question 2 are: None (0) to Extremely Strong (20).

There will be no imputation for missing values.

### **5.2. Alcohol Consumption Endpoints**

#### **5.2.1. Daily Quantity of Alcohol Consumption**

Drinking will be assessed using the TLFB methodology and Form 90 structured assessment pattern chart. The TLFB is a semi-structured interview that provides estimates of the daily quantity of alcohol consumption during specified time periods. It uses a calendar prompt and a number of other memory aids (e.g., holidays, payday, and other personally relevant dates) to facilitate accurate recall of drinking or other drug use during the target period. The procedure has been widely used in clinical and research contexts. It has demonstrated adequate levels of reliability and validity when administered as an in-person interview, over the telephone, and when administered via computer ([Carey-1997](#), [Sobell et al-1988](#), [Sobell et al-1996](#)).

If a subject is withdrawn from the study early and is no longer participating in clinic visits or providing TLFB drinking data but is willing to be contacted by phone at the week most proximal to dropout, then they will be asked about any drinking and heavy drinking during the time since last contact. Phone calls will continue until the end of the treatment period, as deemed acceptable by the patient. The two questions cover whether the subject had any heavy drinking days or drinking days during the period covered and will be used to capture drinking data in the absence of individual daily TLFB drinking data.

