### **5.2.8. World Health Organization Drinking Risk Categorical Scale**

The WHO has developed a drinking risk categorical scale that can be used in a responder analysis approach to assess clinically relevant decreases in alcohol consumption ([Aubin et al-2015](#)). Two dichotomous endpoints will be analyzed: WHO 1-level and WHO 2-level decrease in alcohol consumption. The WHO 1-level and 2-level decrease endpoints are the percentage of subjects experiencing at least a 1-level or 2-level decrease in WHO levels of alcohol consumption, respectively, from the level at baseline (the period including the 28 days before screening) to the level during the last 4 weeks of the maintenance phase (Study Weeks 2-5). The WHO levels of average alcohol consumption per day are as follows:

	Males	Females
Low Risk	1 to 40g	1 to 20g
Medium Risk	41 to 60g	21 to 40g
High Risk	61 to 100g	41 to 60g
Very High Risk	101+g	61+g

where 14g = 1 SDU ([WHO-2000](#)). In computing the alcohol consumption level, average drinks per day will be used, computed as the sum of all drinking in the 28 day period divided by the number of days with non-missing drinking data in that period. Abstinent subjects will be included in a separate “Abstinent” category. A subject must have at least 1 week of data during the last 4 weeks of the maintenance phase to be considered non-missing.

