**12. TABLE, LISTING, AND FIGURE SHELLS**

**12.1. Tables**

**12.1.1. Subject Disposition, Participation, Compliance**

**Table 1: Subject Disposition - All Randomized Subjects**

	ASP8062 n (%)	Placebo n (%)	Total n (%)	p-value 
Number of Subjects Consented			xx	
Number of Subjects Screen Failed			xx	
Number of Subjects Randomized 	xx	xx	xx	0.xxx
Number of Subjects Randomized not Receiving Study Drug	x (xx.x)	x (xx.x)	x (xx.x)	0.xxx
Number of mITT Subjects	xx (xx.x)	xx (xx.x)	xxx (xx.x)	0.xxx
Number of Completed  Subjects	xx (xx.x)	xx (xx.x)	xxx (xx.x)	0.xxx
Number of Evaluable Subjects	xx (xx.x)	xx (xx.x)	xxx (xx.x)	0.xxx
Number of Subject Completing Study & Drug	xx (xx.x)	xx (xx.x)	xx (xx.x)	0.xxx
Number of Subjects Discontinuing Study Drug, Remaining in Study	xx (xx.x)	xx (xx.x)	xx (xx.x)	0.xxx
Number of Subjects Withdrawn Early (did not provide any data at Week 7)	xx (xx.x)	xx (xx.x)	xx (xx.x)	0.xxx
Reason for Early Withdrawal 				
Subject withdrew consent	xx (xx.x)	xx (xx.x)	xx (xx.x)	
Investigator withdrew subject	xx (xx.x)	xx (xx.x)	xx (xx.x)	
Lost-to-followup	xx (xx.x)	xx (xx.x)	xx (xx.x)	
Adverse Event	xx (xx.x)	xx (xx.x)	xx (xx.x)	
Increased drinking	xx (xx.x)	xx (xx.x)	xx (xx.x)	
Psychiatric crisis	xx (xx.x)	xx (xx.x)	xx (xx.x)	
Died	xx (xx.x)	xx (xx.x)	xx (xx.x)	
Absent from the protocol due to confinement in a controlled environment	xx (xx.x)	xx (xx.x)	xx (xx.x)	
Determined after randomization to be ineligible	xx (xx.x)	xx (xx.x)	xx (xx.x)	

Notes:  p-value from Fisher's exact test.

The following percentages are based upon number randomized

Completed is defined as attending all clinical visits through Week 7 making the subject available for all endpoint analyses

The following categories sum to the number of early withdrawals

*Programmer Notes: The discontinuation reasons are as given on the CRF. Include only the reasons actually used for the subjects in the study. If a subject discontinued, but the specific reason is missing, include 'Missing' as a row in the table. Use the order of discontinuation reasons as presented on the CRF page.*

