**Listing 15: Brief Drinking Questionnaire – mITT Subjects**

Subject ID	Treatment Group	Date of Assessment	Date that the last day of non-missing drinking data was collected by TLFB	This is a period of XX days since the last day of drinking data that was collected by TLFB	Did the subject drink during this period?	How many days during this period did the subject drink?
xxx	ASP8062	ddmmmyyyy	ddmmmyyyy	xx	Yes	xx
	Placebo				No	

Subject ID	Treatment Group	Date of Assessment	How many alcoholic drinks on a typical day?	How many heavy drinking days?	Maximum number of drinks on any one day?	How many days did you drink this maximum number?
xxx	ASP8062	ddmmmyyyy	xx	xx	xx	xx
	Placebo					

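### SAP 9.5 says logistic regression handles missing data, but the WHO responder models are complete-case, and no rule says how drinking reported by phone after withdrawal counts

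*SAP*

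**What the plan says.** **Calls after withdrawal.** Under SAP 5.2.1, a subject who withdraws and stops giving timeline follow-back (TLFB) data may be phoned until the end of treatment. The section says: "The two questions cover whether the subject had any heavy drinking days or drinking days during the period covered". The answers "will be used to capture drinking data in the absence of individual daily TLFB drinking data", but no endpoint is named.

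**What the form appears to hold.** Listing 15 (Brief Drinking Questionnaire) has columns for the days elapsed since the last TLFB day, "How many days during this period did the subject drink", "How many alcoholic drinks on a typical day" and "How many heavy drinking days", plus the maximum on one day and the days at that maximum. The only summary table, Table 15, counts how many subjects used the questionnaire.

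**How the endpoints are built.** In SAP 5.2.8 the WHO level is total drinking in the 28-day period divided by the days with non-missing drinking data, at 14 g per drink. "A subject must have at least 1 week of data during the last 4 weeks of the maintenance phase to be considered non-missing". The weekly endpoints in 5.2.6 and 5.2.7 treat a week with fewer than 3 observed days as missing.

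**Missing data.** SAP 9.4.3.1 analyses the WHO endpoints by logistic regression without imputation. SAP 9.5 justifies this: "Secondary endpoints analyzed with mixed effects or logistic regression models are capable of handling missing data, so no imputation will be utilized". Its next sentence accepts that ANCOVA cannot do so.

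**Window.** SAP 9.4.3 and Tables 70, 72 and 73 use Weeks 3-6. SAP 5.2.8, SAP 9.4.3.1 and Table 71 use Weeks 2-5 for the WHO endpoints.

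**The concern.** A logistic model with one record per subject has nothing to borrow from when the outcome is missing; the subject is left out. The 9.5 statement is defensible for the likelihood-based mixed models, under missing at random, but not for the WHO models. A reader of 9.5 would think the WHO analysis is protected against dropout when it is not.

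The second part is the phone data. Yes/no answers cannot produce grams per day, drinks per week or percent heavy days when the answer is yes. The counts in Listing 15 could, at least roughly, but nothing says whether or how they enter. If they do not, a subject who relapses after withdrawal can be scored as a WHO responder on earlier days alone. If the choice is left open, it will be made once data are in hand. The Table 1 disposition shell offers "Increased drinking" as a reason for withdrawal, so the plan itself foresees withdrawals linked to the outcome.

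**Working it through.** The plan gives no figure on this point to reproduce. The check is a reading of the rules plus an illustration using the SAP's formula and cut-points.

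**1. Who is affected.** The modified intention-to-treat (mITT) set requires a non-missing primary craving score (SAP 4), so only withdrawals at or after the Week 3 cue session matter here.

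**2. Is a subject last seen at the Week 3 visit dropped?** Inputs: that visit falls on Days 15 to 21 (schedule of assessments); the WHO minimum is 1 week (5.2.8). Assume that TLFB runs to the day before the visit, so the last observed day is Day 14 to Day 20.
- Weeks 3-6 start on Day 15: 14 - 14 = 0 to 20 - 14 = 6 days. Below 7, so dropped.
- Weeks 2-5 start on Day 8: 14 - 7 = 7 to 20 - 7 = 13 days. At least 7, so kept, but classed on those days alone.

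**3. Classification of a subject who withdraws later.** Male cut-points in 5.2.8: Low 1-40 g, Medium 41-60 g, High 61-100 g, Very High 101 g or more. Assumed subject:
- Baseline: 8 drinks/day x 14 = 112 g, Very High.
- One TLFB week in the window, 28 drinks: 28/7 x 14 = 56 g, Medium. This is a 2-level decrease, so a responder on both endpoints.
- Phone report for the other 21 days, 18 drinking days at 10 drinks: 180 drinks. Then (28 + 180)/(7 + 21) = 208/28 = 7.43 drinks/day, x 14 = 104 g, Very High. A responder on neither.

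**4. Range.** Same baseline, TLFB drinking at 2 drinks/day (28 g, Low, a 3-level decrease on TLFB alone), then daily drinking at r drinks for the rest of the 28 days. Mean grams = 14 x [2d + r(28 - d)]/28, where d is the number of TLFB days.

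| d | r = 4 | r = 6 | r = 8 | r = 10 |
|---|---|---|---|---|
| 7 | 49 g (2 levels) | 70 g (1) | 91 g (1) | 112 g (0) |
| 14 | 42 g (2) | 56 g (2) | 70 g (1) | 84 g (1) |
| 21 | 35 g (3) | 42 g (2) | 49 g (2) | 56 g (2) |

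The 2-level result changes from 6 drinks/day after 7 TLFB days and from 8 after 14 days, and never after 21 days in this grid. The 1-level result changes in one cell only.

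**5. Effect on an arm, with 30 per arm and assumed counts.**
- Misclassified responders: each moves the rate by 1/30 = 3.3 points. From 10/30 = 33.3%, one to three give 9/30 = 30.0% to 7/30 = 23.3%.
- Dropped non-responders: with 15 responders of 30 (50.0%), losing one to three non-responders gives 15/29 = 51.7% to 15/27 = 55.6%.

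**The case against.** Several tempting stronger readings fail.

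- *A reader might infer that subjects last seen at Week 3 are dropped from both WHO models.* That holds only for Weeks 3-6. Under the Weeks 2-5 window, which stands in the same section as the 1-week minimum, they are kept.
- *A reader might infer that the SAP discards the phone data or builds the WHO level from TLFB alone.* It does not say so. Section 5.2.8 refers to non-missing drinking data, and 5.2.1 says the calls are meant to capture drinking. The defect is an absent rule, not an exclusion.
- *A reader might infer that the counts are certainly in the database.* They appear in one listing shell. Other shells hold text that does not fit this trial, such as a different compound in Table 108 and a Week 2 cue visit in Listing 16. Listing 15 may be carried over and 5.2.1 correct; the case report form is not among the documents.
- *A reader might infer that the loss is shown to depend on drinking.* A tick-box reason in a disposition table shows possibility, not frequency, and an increase known at withdrawal may already be in the TLFB.

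There are also recovery routes. The schedule's footnote on the end-of-study visit offers that visit, with TLFB, to subjects who leave early and agree to attend, and 5.2.6 lets TLFB fill missed periods at a later visit. The unrecovered gap is subjects who give no further TLFB, whether or not they take calls.

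The protocol rules out imputation for secondary endpoints. Using a subject's own phone report in a 28-day average is not plainly imputation, but spreading it over individual weeks comes close.

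What stands: the logistic statement in 9.5 is wrong, 5.2.1 and Listing 15 disagree, and no derivation rule exists.

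**Conclusion.** The concern holds as a correction to a stated rule and as a gap in derivation. The WHO logistic models are complete-case. Subjects with under a week of data are lost, and later withdrawals whose TLFB is not recovered are classed on earlier days unless a phone rule is written. Post-withdrawal drinking that was collected may therefore not count.

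The size cannot be stated: no dropout rate is given, and every patient and count in the illustration is assumed. Per affected subject the shift is about 3.3 points in an arm of 30, mainly on the 2-level endpoint and for withdrawal early in the window. The comparison between arms is biased only if withdrawal, or drinking after it, differs by arm. These are secondary endpoints without multiplicity adjustment; the primary craving analysis is untouched. The change should be made, but it does not threaten the trial's main result.

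**What to change.** 1. In SAP 9.5, remove logistic regression from the sentence on handling missing data, and state that the WHO logistic models are complete-case.
2. Reconcile 5.2.1 with Listing 15 against the case report form, and say how each item enters each drinking endpoint or that it is for listing only.
3. Reconcile the two WHO windows across 5.2.8, 9.4.3, 9.4.3.1 and Tables 70 to 73.
4. Keep the main WHO definition and pre-specify two sensitivity analyses:
   - (a) If the form records the counts: average drinks/day = (TLFB drinks + phone drinking days x typical drinks) / (TLFB days + phone-period days), with phone days counting toward the 1-week minimum.
   - (b) mITT subjects with no TLFB or phone data after withdrawal counted as non-responders.
5. Optionally, rerun the mixed models for the weekly drinking endpoints with phone-period rates in the weeks they cover.

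The cost is SAP wording and programming, with no new calls if the counts are already on the form; if they are not, (a) and item 5 fall away. Phone counts are coarser than TLFB, typical drinks need a stated conversion to standard drinks, and weekly allocation is close to imputation. For those reasons these should remain sensitivity analyses.
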